9.1 Definition of Baseline and Change from Baseline

If not otherwise specified, 'baseline' refers to the last scheduled measurement before administration of first study intervention.

However, if a participant is missing the baseline collection, the previous non-missing evaluation could become the baseline value (e.g. from screening/admission). If no baseline or previous to baseline evaluations exist, then the baseline value will be treated as missing.

Absolute changes from baseline are defined as

$$\text{absolute change} = \text{visit value} - \text{baseline value}$$

9.2 Study Day / Study Intervention Day

Day 1 is the day of start of study intervention, the day before is Day -1 (no Day 0 is defined). Study day is defined relative to Day 1.

9.3 Definition of Duration and 'Time Since' Variables

The following definitions and calculations of duration, as applicable, will be applied:

- Duration of adverse event (AE) (in days hh:mm) = end date and time - start date and time of the AE, if missing time for either the beginning or end then = end date - start date + 1; in case of multiple records for the same AE, the duration will be calculated over all these records

- Days hh:mm from dosing (onset post administration) = start date and time of the event - date and time of last dose administration of tepotinib or itraconazole (calculated for each intervention, for TEAEs), if missing time for either the dosing or event then days hh:mm from dosing = event start date – date of dose administration + 1
- Relative (Rel.) Day in study of AE = start date of the event – date of first admin + 1 (for AEs on or after the day of dosing)
- Rel. Day in study of AE = start date of the event – date of first admin (for events before the day of dosing of the study only)

9.4 Imputation of Missing Data

In this Phase I PK study, missing observations will be assumed to be missing completely at random (MCAR). No action will be taken to handle missing data. A participant who withdraws prior to the last planned observation in a study period will be included in the analyses up to the time of discontinuation.

10 Study Participants

The subsections in this section include specifications for reporting participant disposition and study intervention/study discontinuations. Additionally, procedures for reporting protocol deviations are provided.

10.1 Disposition of Participants and Discontinuations

The following will be presented in a summary table:

- Total number of participants screened (i.e., participants who gave informed consent)
- Number of screened participants who discontinued from the trial prior to first dosing overall and grouped by the main reason for discontinuation:
 - Participant did not meet all eligibility criteria
 - Withdraw consent
 - Other (COVID-19-related and COVID-19-non-related)
- Number of treated participants
- Number and percentage of treated participants who completed study
- Number and percentage of treated participants who discontinued the study or study intervention, with the primary reason of discontinuation:
 - Adverse event
 - Lost to follow-up
 - Protocol non-compliance
 - Death

- Withdrew consent
- Other (COVID-19-related and COVID-19-non-related)

The number and percentage of participants will be presented by group of study intervention and total, where applicable. Percentages will be presented with respect to the number of treated participants, where applicable.

A listing of discontinued participants will be provided.

A listing of participants affected by the COVID-19 related study disruption by unique participant identifier will also be provided.

10.2 Protocol Deviations / Exclusion from Analysis Sets

10.2.1 Important Protocol Deviations

Listings of important protocol deviations will be provided including the date and relative day in relation to first dosing in the study. A distinction will be made between important protocol deviations due to COVID-19 versus not due to COVID-19. The respective important protocol deviations will be flagged accordingly.

Important protocol deviations or important events that might have an effect on PK include, but may not be limited to the following:

- Adverse events like diarrhea etc. (these instances will be discussed on a case-by case basis)
- Vomiting after administration following oral dosing (these instances will be discussed in alignment with applicable regulatory guidelines on a case-by case basis)
- Sample processing errors that may lead to inaccurate bioanalytical results
- Inaccurate dosing or dosing errors (e.g. dose administration delayed, dose change or missed doses)
- Pre-dose or trough sample collected after the actual dosing
- Non-compliance with food and drink requirements (e.g. non-fasted, incomplete meal consumption, caffeine intake)
- Concomitant medication, vitamins, dietary or herbal supplements

Should one or more of these events be available at the Data Review Meeting, its implication for PK evaluation will be discussed and agreed amongst relevant study team members (e.g. Sponsor Clinical Pharmacology/Biostatistics/Clinical Pharmacokinetics & Pharmacodynamics team representative). Appropriate action will be taken such as flagging individual values to be excluded from analysis.

10.2.2 Reasons Leading to the Exclusion from an Analysis Set

If participants are excluded from the PK Analysis Set, the reasons for exclusion will be listed.

Reasons for excluding individual PK concentrations will also be listed separately and flagged in the main listing.

11 Demographics and Other Baseline Characteristics

Demographics and baseline characteristics will be presented for the SAF.

11.1 Demographics

Descriptive statistics will be presented for age, height, weight, and body mass index (BMI). Frequency counts and percentages will be presented for sex, race, and ethnicity. The summary will be performed overall.

BMI (kg/m²) will be derived (i.e., not taken directly from the database) according to the following formula:

$$\text{BMI [kg/m}^2\text{]} = \frac{\text{weight [kg]}}{\text{height[cm]}^2} \times 10000$$

11.2 Medical History

Medical history will be coded using the Medical Dictionary for Regulatory Activities (MedDRA), most current version at time of data base lock, and listed.

The medical history will be listed by participant including preferred term (PT) as event category and system organ class (SOC) body term as Body System category.

11.3 Other Baseline Characteristics

Other baseline measurements, such as virus screen, alcohol and drugs of abuse screen, pregnancy test in women, nicotine and alcohol consumption, will be listed.

Baseline characteristics with respect to vital signs, physical examinations, and hematology/biochemistry will be part of Section 15 (Safety Analysis).

12 Previous or Concomitant Therapies/Procedures

Medications will be presented for the SAF.

Previous medications are defined as any medication discontinued prior to the administration of first study intervention. Concomitant medications are defined as any medication taken during the course of the study, with a starting date greater than or equal to the administration of first study intervention, or with a starting date prior to the administration of first study intervention and ongoing at the time of the first administration of study intervention.

The World Health Organization Drug dictionary (WHO-DD), most current version at time of database lock, will be used for coding of prior and concomitant medications and they will be described using Preferred Term (PT) as applicable.

Previous and concomitant medications will be listed. Concomitant procedures, if any, will also be listed.

13 Study Intervention: Compliance and Exposure

The dosing of each participant is monitored by the study nurse or investigator. A listing of date and time of each drug administration and each blood sampling, including time deviations as well as measured plasma concentrations, will be provided sorted by participant. Information on meal intake will be listed by participant, if provided.

14 Efficacy Analyses

Not applicable.

15 Safety Analyses

This section includes specifications for summarizing safety endpoints that are common across clinical studies such as adverse events, laboratory tests and vital signs.

All safety analyses will be performed for the Safety Analysis Set and will be presented by study intervention and nominal timepoint, as appropriate.

Safety analyses will be done according to the as-treated principle.

15.1 Adverse Events

All AEs recorded during the course of the study will be coded with the MedDRA, latest version at time of data base lock, and assigned to a SOC and a PT.

Treatment-emergent AEs (TEAEs) are those events with onset dates on or after the first administration of study intervention on Day 1. Any AE occurring before the administration of study intervention on Day 1 and resolved before administration of study intervention or not worsening after administration of study intervention on Day 1 will be included in the AE listings but will not be included in the summary tables (unless otherwise stated). These will be referred to as “pre-treatment” AEs. An AE occurring after administration of any study intervention will be counted towards the last intervention received before the onset, even if the event is not resolved at the beginning of the following intervention. An AE that worsens after a later intervention period will be counted towards both study interventions.

In case AE-related dates are partial, the available information will be used in a conservative approach to determine whether the AE is treatment-emergent.

All analyses described in Section 15.1 will be based on TEAEs if not otherwise specified. The AE listings will include all AEs (whether treatment-emergent or not). AEs outside the on-treatment period will be flagged in the listings.

Unless otherwise specified, TEAEs will be summarized, by number and percentage of participants with the TEAE in the category of interest, as well as the number of events, in total and by study intervention group, primary SOC and PT in alphabetical order for SOC and decreasing overall frequency for PT.

Each participant will be counted only once within each SOC or PT.

If an event was reported more than once due to change in intensity and change in relationship, the worst severity and the worst relationship to trial treatment will be tabulated.

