8.3 Adverse Events, Serious Adverse Events, and Other Safety Reporting

- The definitions of an AE and a SAE are in [Appendix 4](#).
- The Investigator and any qualified designees (e.g., Sub-Investigators) are responsible for detecting, documenting, and recording events that meet the definition of an AE or SAE. The Investigator remains responsible for following up AEs that are serious, considered related to the study intervention or study procedures, or that caused the participant to discontinue the study intervention or study, as specified in Section 8.3.2.

- Requests for follow-up will usually be made via the Sponsor or CRO-designated study team member, although in exceptional circumstances the global patient safety department may contact the Investigator directly to obtain further information or to discuss the event.
- The method of recording, evaluating, and assessing causality of AEs and SAEs and the procedures for completing and transmitting SAE reports are in [Appendix 4](#).
- All AEs and SAEs will be collected from the signing of the ICF until the Safety Follow Up Visit at the time points specified in the Schedule of Assessments (Section 1.3). Beyond this reporting period, any new unsolicited SAEs that the Investigator spontaneously reports to the Sponsor will be collected and processed.
- All SAEs will be recorded and reported to the Sponsor or designee immediately and under no circumstance will this exceed 24 hours, as indicated in [Appendix 4](#). The Investigator will submit any updated SAE data to the Sponsor within 24 hours of it being available using the same procedure that was used for the initial report.
- Investigators are not obligated to actively solicit information on AEs or SAEs after the end of study participation. However, if the Investigator learns of any SAE, including a death, at any time after a participant has been discharged from the study, and he/she considers the event to be reasonably related to the study intervention or study participation, the Investigator will promptly notify the Sponsor.

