- Any abnormal laboratory test results (hematology, clinical chemistry, or urinalysis) or other safety assessments (e.g., ECG, radiological scans, vital signs measurements), including those that worsen from baseline and are judged to be more severe than expected for the participant's condition are considered clinically significant in the medical and scientific judgment of the Investigator (i.e., not related to progression of underlying disease, but may be leading to study intervention discontinuation).
- Exacerbation of a chronic or intermittent preexisting condition including either an increase in frequency and/or intensity of the condition.
- New conditions detected or diagnosed after study intervention administration even though it may have been present before the start of the study.
- Signs, symptoms, or the clinical sequelae of a suspected drug-drug interaction.
- Signs, symptoms, or the clinical sequelae of a suspected overdose of either study intervention or a concomitant medication.
- “Lack of efficacy” or “failure of expected pharmacological action” per se will not be reported as an AE or a SAE. However, the signs, symptoms, and/or clinical sequelae resulting from lack of efficacy will be reported as an AE or a SAE if they fulfil the definition of an AE or SAE.

Events NOT Meeting the AE Definition

- Unless judged by the Investigator to be more severe than expected for the participant's condition, any clinically significant abnormal laboratory findings, other abnormal safety assessments that are associated with the underlying disease, the disease/disorder being studied within the expectedness for participant's condition, as judged by the Investigator.
- Medical or surgical procedure (e.g., endoscopy, appendectomy): the condition that leads to the procedure is the AE.
- Situations in which an untoward medical occurrence did not occur (social and/or convenience admission to a hospital).

- Anticipated day-to-day fluctuations of preexisting disease(s) or condition(s) present or detected at the start of the study that do not worsen.

SAE Definition

If an event is not an AE per the definition above, then it cannot be an SAE even if serious conditions are met (e.g., hospitalization for signs/symptoms of the disease under study, death due to progression of disease).

A SAE is defined as any untoward medical occurrence that, at any dose:

a. Results in death

b. Is life-threatening

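### SAP 15.1 leaves an adverse event that starts before dosing and worsens after the Day 1 dose neither treatment-emergent nor pre-treatment, with no intervention column

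*SAP*

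**What the plan says.** SAP 15.1 (Adverse Events) contains five rules that bear on this point.

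- **TEAE definition:** "Treatment-emergent AEs (TEAEs) are those events with onset dates on or after the first administration of study intervention on Day 1". It has no worsening clause.
- **Pre-treatment AEs:** a pre-dose AE that "resolved before administration of study intervention or not worsening after administration of study intervention on Day 1 will be included in the AE listings" is kept out of the summary tables and carries the pre-treatment label.
- **Column assignment:** "An AE occurring after administration of any study intervention will be counted towards the last intervention received before the onset".
- **Later worsening:** an AE that worsens after a later intervention period counts towards both interventions.
- **Basis of the outputs:** unless otherwise specified, every Section 15.1 analysis uses TEAEs. The AE listings show all AEs.

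The protocol names TEAEs as a secondary endpoint (Section 3) but does not define the term. On collection, protocol 8.3 states: "All AEs and SAEs will be collected from the signing of the ICF until the Safety Follow Up Visit". Pre-dose AEs can therefore be on record. Among events that count as AEs, protocol Appendix 4 lists "Exacerbation of a chronic or intermittent preexisting condition including either an increase in frequency and/or intensity of the condition".

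**The concern.** The first two rules sit next to each other and do not divide AEs into complementary classes. The first looks only at onset. The second uses worsening after the first dose to decide whether a pre-dose AE stays out of the tables. A pre-dose AE that worsens after tepotinib falls between them.

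At stake is a correct count for a secondary safety endpoint. Such an event is one that a reader of a tolerability table would expect to see, since it became more intense after study drug. Programmed literally, the section omits it from the incidence, severity and relationship tables in 15.1.1. It also omits it from 15.1.2, where both the listing and the table of events leading to discontinuation are restricted to TEAEs. A programmer who follows the second sentence instead would include the event but would find no rule for its column. Two people working from the same section could produce different tables.

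**Working it through.** The plan gives no figure to reproduce. The check is to list the possible AE states and apply the SAP rules to each.

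**Inputs.** The TEAE, pre-treatment and column rules are from SAP 15.1. The maximum number treated, 18, is from protocol 9.2. The denominator for AE tables, participants in the analysis set who received the intervention, is from SAP 9. The 5% cut-off for the table of frequent non-serious TEAEs is from SAP 15.1.1.

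**Step 1. Classify each state.**

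| Onset | Resolved before dosing | Worsens after Day 1 dose | TEAE | Pre-treatment | Column |
|---|---|---|---|---|---|
| Before first dose | Yes | No | No | Yes | Not needed |
| Before first dose | No | No | No | Yes | Not needed |
| **Before first dose** | **No** | **Yes** | **No** | **No** | **None** |
| After first dose | Not applicable | No | Yes | No | Last intervention before onset |
| After first dose | Not applicable | Yes | Yes | No | Last intervention before onset |

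Four of the five states fall in exactly one class. The third falls in none.

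**Step 2. Look for another rule that catches it.**

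- The column rule needs an intervention before onset. With pre-dose onset there was none.
- The later-worsening rule counts the event towards both interventions, which presupposes that an earlier intervention already carries it.
- SAP 9.3 computes duration across all records of the same AE, and SAP 15.1 tabulates the worst severity when an event is recorded more than once. Neither says which record's start date is the onset.
- The protocol offers no TEAE definition to fall back on.

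**Step 3. Where the event still appears.** It is in the AE listings, which cover all AEs. The SAE table (SAP 15.2.2) and the AESI table (SAP 15.2.3) are not restricted to TEAEs, so a serious event or an AESI is counted there.

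**Step 4. Size.** One participant in a full column is 1/18 = 5.6%. Any column of 20 or fewer gives at least 1/20 = 5%, so one participant is enough to bring a non-serious preferred term into the frequent-TEAE table.

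**Step 5. Recheck under the fix.** With worsening after the first dose added to the TEAE definition, and attribution to the last intervention before the worsening, the third state becomes a TEAE with a column. All five states then fall in exactly one class.

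**The case against.** The strongest reply is that the second sentence already shows what was meant. Excluding only pre-dose AEs that resolved or did not worsen makes sense only if worsened ones go in. That is a fair reading of intent, and it stands: a reader might infer that the SAP chose to omit these events, but the text contains no such decision. The reply does not remove the problem, because the TEAE definition and the TEAE-only basis of the outputs say otherwise, and inclusion would still leave the event without a column.

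A second reply is that protocol Appendix 4 treats exacerbation as an AE in its own right, so the worsening could be recorded as a new event with a post-dose start date and qualify as a TEAE. This could happen in practice. However, the SAP treats several records as one AE and does not say which start date governs, so the reply mitigates the gap without closing it.

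A third reply is that little is lost: the listings are complete, the 15.2 tables capture SAEs and AESIs, and at most 18 listings can be read by eye. This also stands, and it limits the importance of the point.

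Three stronger readings are tempting and are not supported:

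- A reader might infer that the omission biases a comparison of tepotinib alone with the combination. Protocol 9.1 makes the analysis purely descriptive, and the Day 12 versus Day 1 contrast is a PK contrast. No document makes tepotinib alone the reference for AE rates.
- A reader might want a probability that at least one such event occurs. The documents give neither a rate of AEs ongoing at dosing nor a rate of worsening, so any figure would only reflect the rates assumed.
- A reader might see a second conflict for an AE that starts on Day 1 before the dose. The TEAE sentence is anchored to the administration, the next sentence deals separately with AEs before it, and SAP 9.3 works with AE start times. That reading is weak.

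**Conclusion.** The two sentences of SAP 15.1 are inconsistent. Read literally, they leave one AE state out of the TEAE-based outputs of 15.1 and 15.1.2, contrary to the evident intent of the second sentence. The conclusion rests on the wording alone and on no assumed event rate.

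The expected number of affected events is unknown. It is probably small: protocol 5.1 requires participants to be overtly healthy at both Screening and Day -1, with laboratory values normal apart from minor excursions. Each affected participant is nevertheless 5.6% of a column of 18, and a larger share if fewer receive the intervention. The AE listings, the SAE and AESI tables in 15.2 and the primary PK analysis are unaffected. The point is a definitional error worth correcting before database lock, and it does not threaten the trial's main conclusion.

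**What to change.** In SAP 15.1, replace the TEAE definition with wording to this effect: *TEAEs are AEs that start at or after the first dose on Day 1, or that start earlier and increase in intensity after that dose.* Add to the attribution rule: *An AE with pre-dose onset that worsens is attributed to the last intervention received before the worsening.*

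The pre-treatment sentence can stay as it is, since it then complements the definition. The cost is two sentences of SAP text and one programming flag. The downside is that a few more events may enter the TEAE tables.

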15.1.1 All Adverse Events

Number of treatment-emergent AEs and participants experiencing TEAEs will be summarized for Tepotinib, Itraconazole, Itraconazole+Tepotinib and overall, each in tables with:

- The number and percentage of participants with any TEAE, any related TEAE, any tepotinib-related TEAE, any itraconazole-related TEAE, any serious TEAE, any related serious TEAE, any tepotinib-related serious TEAE, any itraconazole-related serious TEAE, any severe TEAE, any related severe TEAE, any tepotinib-related severe TEAE, any itraconazole-related severe TEAE, any AEs of special interest (AESI), any TEAE leading to death, any related TEAE leading to death, any tepotinib-related TEAE leading to death, any itraconazole -related TEAE leading to death, any TEAE leading to study discontinuation
- The number and percentage of participants with at least one TEAE and the number of events by SOC and PT.
- The number and percentage of participants with TEAEs excluding SAEs and number of events, with frequency of participants $\geq 5\%$ in any study intervention arm by SOC and PT
- The number and percentage of participants with at least one TEAE and number of events by severity, SOC, and PT
- The number and percentage of participants with at least one related TEAE, tepotinib-related TEAE, itraconazole -related TEAE and number of events by SOC and PT
- The number and percentage of participants with at least one AESI recorded and number of events by SOC and PT.

Unless otherwise stated, AEs will be displayed with SOC terms sorted alphabetically and PTs within each SOC term sorted in descending overall frequency.

For determining incidence counts, within each level of TEAE term, if a participant experiences more than one occurrence, the participant will only be counted once for that TEAE.

Adverse events related to any study intervention are those events with relationship missing, unknown or yes.

In case a participant had events with missing and non-missing severity, the maximum non-missing severity will be displayed.

